9.10.7.1 Clinical Chemistry

For Part 1 of the study, clinical chemistry will be performed at screening, in the morning on Day -1, and on Day 4. For Part 2 of the study, clinical chemistry will be performed at screening, in the morning on Day -1, and on Days 5, 10, and 16. The following will be assessed: albumin, alkaline phosphatase, AST, ALT, urea, calcium, chloride, glucose, phosphorus, potassium, creatinine, sodium, bicarbonate (CO₂), total bilirubin, indirect bilirubin, CPK, direct bilirubin, and total protein.

Considering that indirect bilirubin is calculated from total and direct bilirubin values, indirect bilirubin result would not be available in case of direct bilirubin below the limit of quantification.

Estimated glomerular filtration rate (eGFR) will be calculated by the MDRD4 Equation at screening.

9.10.7.2 Serology

HBsAg, HCV antibody, and HIV antigen and antibody detection will be performed at screening.

9.10.7.3 Hematology

For Part 1 of the study, hematology will be performed at screening, in the morning on Day -1, and on Day 4. For Part 2 of the study, hematology will be performed at screening, in the morning on Day -1, and on Days 5, 10, and 16. The following will be assessed: complete blood count with differential, hemoglobin, and hematocrit.

9.10.7.4 Coagulation

For Part 1 of the study, coagulation tests (PT, aPTT, and INR) will be performed at screening, in the morning on Day -1, and on Day 4. For Part 2 of the study, coagulation tests will be performed at screening, in the morning on Day -1, and on Day 16. The following will be assessed: prothrombin time/international normalized ratio (PT/INR) and activated partial thromboplastin time (aPTT).

9.10.7.5 Urinalysis

For Part 1 of the study, urinalysis will be performed at screening, in the morning on Day -1, and on Day 4. For Part 2 of the study, urinalysis will be performed at screening, in the morning on Day -1, and on Day 16. The following will be assessed: macroscopic examination, pH, specific gravity, protein, glucose, ketones, bilirubin, occult blood, nitrite, urobilinogen, and leukocytes. Unless otherwise specified, microscopic examination will be performed on abnormal findings.

9.11 Discharge/Study Exit Procedures

For Part 1 of the study, the following will be performed on Day 4: brief physical examination, vital signs, body temperature, ECG, pulse oximetry, clinical chemistry, hematology, coagulation, urinalysis, PK sample, urine and serum pregnancy test (females only), and adverse events monitoring.

For Part 2 of the study, the following will be performed on Day 16: brief physical examination, vital signs, body temperature, ECG, pulse oximetry, clinical chemistry, hematology, coagulation, urinalysis, PK sample, urine and serum pregnancy test (females only), WI-NRS, and adverse events monitoring. The following will be performed on Day 17: PK sample.

If not possible, all efforts will be made to complete study exit procedures within 14 days after the last participation of the subject in the study.

In the case that a subject experiences a DLT or a DLT dose is confirmed in 2 subjects during Part 2 (MAD), post last-dose study procedures will be performed as laid out in the DLT Follow-Up Period (see Section [9.11.1](#)). Early Termination procedures are only applicable to subjects who discontinue study drug for reasons other than those related to DLT.

9.11.1 DLT Follow-Up Period for Part 2 (MAD), Post-Last Dose

In Part 2 of the study, any subject who experiences a DLT TEAE will not receive further dose of study drug, and safety follow-up procedures, per the DLT Follow-Up Period will be performed.

If 2 subjects develop a DLT, all subjects who are currently receiving a confirmed DLT dose will not receive further dose of study drug and will immediately enter into the DLT Follow-Up Period.

The maximum safe dose (MSD) will be determined as the dose level below the DLT dose.

Subsequent subjects in Part 2 of the study will only be dosed through the completion of the MSD per the days specified in the titration table. After dosing is complete, subjects will immediately enter the DLT Follow-Up Period and the following procedures will be performed:

DLT Follow-Up Period Procedures

- Subjects will be confined until after the 72-hour post-last dose blood draw and will come back for the final 96-hour post-last dose blood draw the following day at the Study Exit visit.
- Vital signs (blood pressure, heart rate, and respiratory rate): pre-last dose and approximately 1, 2, 4, 6, 8, and 12 hours post-last dose, and once a day until end of confinement.
- 12-lead ECG: pre-last dose and approximately 1, 2, 4, 6, 8, and 12 hours post-last dose and once a day until end of confinement.
- PK blood samples: a total of 12 blood samples will be collected for the last dose: at pre-last dose and 1.5, 3, 5, 7, 9, 12, 24, 36, 48, 72, and 96 hours post-last dose.
- Oxygen saturation via pulse oximetry will be measured: pre-last dose and at 1.5, 4.5, and 8 hours following the last dose (if morning dose), and at 2 hours following the last dose (if evening dose). Pulse oximetry measurements may be collected within 10 min before or after the specified time point. Oxygen saturation will be monitored via pulse continuous oximetry beginning at bedtime and continuing overnight until waking time through end of confinement with oxygen saturation measurements specifically recorded at approximately midnight and 4 am.
- WI-NRS will be performed on a daily basis, to be collected twice per day until end of confinement: once within an hour (+/- 1 hour) of completing their morning and evening meals, if applicable. Subjects will fill in the “Nighttime Itch” form in the morning and the “Daytime Itch” form in the evening.
- Laboratory assessments (ie, clinical chemistry, hematology, coagulation, and urinalysis) will be done in the morning prior to discharge following a fasting period of at least 8 hours.
- Urine and serum pregnancy tests will be performed prior to discharge (as applicable).
- Brief physical exam will be performed and body temperature will be taken prior to discharge.
- Subjects will be monitored by the study staff for adverse events and concomitant medications until study exit.

DLT Follow-Up Procedures are to be completed at the time points specified wherever feasible, though this may not be possible in some circumstances, including: if the last dose occurs in the evening (eg. for a subject who experiences a DLT) and time points are during the sleep period; and/or the AE leading to DLT occurs after a procedure time point has passed (for example, if a DLT occurred 2 hours post-dose on Study Days 2-12, ECG would not have been performed 1 hour post-dose).

9.11.2 Early Termination for Part 2 (MAD)

In Part 2 of the study, Early Termination follow up procedures are only applicable to subjects who discontinue study drug for reasons other than those related to DLT (see Section [9.11.1](#)).

Early termination follow up procedures are to be completed at the time points specified wherever feasible, though this may not be possible in some circumstances, including: if the last dose occurs in the evening and time points are during the sleep period; and/or the subject is withdrawn from the study after a procedure time point has passed.

The following procedures will be performed (unless consent is withdrawn):

- Vital signs (blood pressure, heart rate, and respiratory rate) should be collected prior to discharge.
- 12-lead ECG should be collected prior to discharge.
- PK blood samples will be collected until the time of discharge for the last dose administered at pre-last dose and 1.5, 3, 5, 7, 9, 12, 24, 36, 48, 72, and 96 hours post-last dose.
- Oxygen saturation via pulse oximetry will be measured until discharge: pre-last dose and at 1.5, 4.5, and 8 hours following the last dose (if morning dose), and at 2 hours following the last dose (if evening dose). Pulse oximetry measurements may be collected within 10 min before or after the specified time point. Oxygen saturation will be monitored via pulse continuous oximetry beginning at bedtime and continuing overnight until waking time through end of confinement with oxygen saturation measurements specifically recorded at approximately midnight and 4 am.
- WI-NRS will be collected twice per day until discharge: once within an hour (+/- 1 hour) of completing their morning and evening meals, if applicable. Subjects will fill in the "Nighttime Itch" form in the morning and the "Daytime Itch" form in the evening.
- Laboratory assessments (ie, clinical chemistry, hematology, coagulation, and urinalysis) will be done in the morning prior to discharge following a fasting period of at least 8 hours (if possible).
- Urine and serum pregnancy tests will be performed prior to discharge (as applicable).
- Brief physical exam will be performed and body temperature will be taken prior to discharge.
- Subjects will be monitored by the study staff for adverse events and concomitant medications until discharge.

9.12 Data Collection and Evaluation

All clinical raw data will be recorded promptly, accurately, legibly, and indelibly by the clinical staff on raw data sheets and/or recorded electronically using validated software and transcribed into case report forms. All raw data will be conserved in order to maintain data integrity. A physician and/or the clinical staff will assume the responsibility of ensuring the completeness and accuracy of the clinical data.

9.13 Subject Withdrawal and Replacement

Subjects will be advised that they are free to withdraw from the study at any time. Over the course of the study, the Sponsor and the Investigator or a delegate may withdraw any subject from the study for one of the reasons described below; subject withdrawal will be done in accordance with SOPs of the clinical sites:

- safety reason;
- non-compliance with protocol requirements;
- significant protocol deviation;
- positive urine alcohol or drug screen, or pregnancy test.

Subjects missing one dose of scheduled IP or experiencing emesis during the study will be evaluated on a case-by-case basis for possible impact on the outcome of the study.

Hematology, clinical chemistry, urinalysis, and coagulation results will be reviewed by an Investigator prior to first dosing; subjects will be withdrawn from the study if it is deemed that the subject's safety may be at risk on the basis of these test results. For subjects with hepatic impairment and taking medications that are allowed by the Investigator, a positive result to opiate/benzodiazepine/THC screen (drug screen) may have derived from these medications and these subjects will not be automatically withdrawn from the study. Subjects who withdraw or are withdrawn from the study after dosing, for reasons other than safety and tolerability, may be replaced after consultation between the Investigator and Sponsor. The total number of subjects dosed (including potential replacement subjects) will remain within a maximum of 112 subjects for the whole study.

Subjects who withdraw or are withdrawn will be asked to remain at the clinic until the Investigator or a delegate agrees that the subject is fine and can be discharged. As soon as subject withdrawal is confirmed, blood sampling will be stopped. A PK blood draw may be collected at the time of withdrawal if deemed required by the Investigator. Study exit procedures will be performed at the time of withdrawal from the study or as soon as possible thereafter.

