Study Design:	
This is a Phase 1, open-label PK and safety study of NAL ER in subjects with impaired hepatic function compared to healthy subjects. It will be performed in 2 parts:
 
 Part 1: single-ascending-dose (SAD) cohorts Part 2: multiple-ascending-dose (MAD) cohort 
Part 1 (SAD) – Dose Cohorts 1 to 5
 
 Cohort 1 (27 mg): 6-8 subjects with mild hepatic impairment, 6-8 subjects with moderate hepatic impairment, and 4-6 subjects with severe hepatic impairment Cohort 2 (54 mg): 6-8 subjects with mild hepatic impairment and 6-8 subjects with moderate hepatic impairment Cohort 3 (108 mg): 6-8 subjects with mild hepatic impairment and 6-8 subjects with moderate hepatic impairment Cohort 4 (162 mg): 6-8 subjects with mild hepatic impairment and 6-8 subjects with moderate hepatic impairment Cohort 5 (highest dose tested in subjects with mild or moderate hepatic impairment): 6-8 healthy control subjects who have been appropriately age-, body mass index (BMI)-, and gender-matched to subjects with mild and moderate hepatic impairment from Cohorts 1 to 4 
In Part 1 of the study (SAD), each of the cohorts will be dosed sequentially starting with the lowest dose for subjects with mild or moderate hepatic impairment. Subjects enrolled in Cohort 1 can also be enrolled in Cohorts 2, 3, and 4.
 
For each dose cohort, enrollment of subjects with mild or moderate hepatic impairment can be done in parallel. An evaluation of safety and tolerability of the combined mild and moderate hepatic impairment subject data will be done at each dose level before proceeding to the next dose level.

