Subjects:	
Up to a maximum of 94 adult male or female subjects, ≥ 18 and ≤ 80 years of age will be enrolled in the study. Subjects with normal hepatic function and hepatic impaired subjects may be non-smokers or light smokers (no more than 5 cigarettes/day).
 
Subjects who withdraw or are withdrawn from the study after dosing, for reasons other than safety and tolerability, may be replaced after consultation between the Investigator and Sponsor. The total number of subjects dosed (including potential replacement subjects) will remain within a maximum of 94 subjects for the whole study.
 
An effort will be made to carefully match the healthy subjects (Cohort 5, SAD) with the subjects with mild and moderate hepatic impairment (Cohorts 1 to 4) by age (± 10 years), BMI ($\pm 15\%$), and gender, to the extent possible. Matching strategy is to enroll control subjects with normal hepatic function who meet demographically matched mean criteria of the pooled subjects with mild and moderate hepatic impairment.
 
The study will enroll up to 8 subjects in Part 2 of the study (MAD) in each of the mild and moderate Child-Pugh categories (a total of up to 16 subjects). An effort will be made to enroll subjects who self-categorize as having some itch (Worst Itch Numerical Rating Scale [WI-NRS] mean score of ≥ 3 at screening). Worst itching intensity scores will be recorded twice daily as specified in the schedule of events. WI-NRS will be used to determine the severity of itch in the hepatic-impaired subjects.

Subject Distribution:	
Cohorts 1 to 4 (Part 1, SAD) will each include the following groups of hepatic-impaired subjects:

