	
 Group 1: Child-Pugh Group A: score 5-6 points; 6-8 subjects with mild hepatic impairment Group 2: Child-Pugh Group B: score 7-9 points; 6-8 subjects with moderate hepatic impairment Group 3: Child-Pugh Group C: score 10-15 points; 4-6 subjects with severe hepatic impairment 
Cohort 5 (Part 1, SAD) will include dosing of healthy subjects with normal hepatic function (control group) to obtain 6-8 subjects who did not vomit within 6 hours of dosing or have any episode of vomiting in order to obtain adequate PK data.
 
The total number of subjects dosed (including potential replacement subjects) will remain within a maximum of 94 subjects for the whole study (up to 78 subjects in the SAD and up to 16 subjects in the MAD). Subjects enrolled in Cohort 1 can also be enrolled in Cohorts 2, 3, and 4. Subjects enrolled in Part 1 can also be enrolled in Part 2.
										
Screening Procedures:	
Demographic data, medical and medication histories, complete physical examination, body measurements, 12-lead electrocardiogram (ECG), vital signs (blood pressure, heart rate, and respiratory rate), pulse oximetry, body temperature, hematology, coagulation (PT, aPTT, and INR), clinical chemistry, human immunodeficiency virus (HIV), hepatitis B and C tests, urinalysis, WI--NRS (Part 2 only), urine and serum pregnancy test (females only), and urine alcohol and drug screen.
 
Assessment of liver function will be performed, and the degree of hepatic impairment will be categorized using Child-Pugh system at screening.
										
Confinement and Washout:	
Part 1 (SAD)
 
Subjects in Cohorts 1 to 4 will be confined from the morning of Day -1 until Day 4 (after the 72-hour post-dose blood draw).
 
Cohort 5 subjects will be confined from the morning of Day -1 until Day 3 (after the 48-hour post-dose blood draw). Subjects will come back to the clinic on Day 4 for the final blood draw and safety procedures at the study exit visit.
 
There will be a washout period of at least 7 days between each administration of the investigational product (IP) in Part 1 of the study and between Parts 1 and 2 of the study.
 
Part 2 (MAD)
 
Cohort 6 subjects will be confined from the morning of Day -1 until Day 16 (after the 72-hour post-last dose blood draw). Subjects will come back on Day 17 for the final blood draw (96-hour post-last dose blood draw) at the Study Exit visit.
										

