Dose Escalation Stopping Rules:	
Dose escalation can be stopped if any treatment-emergent adverse event (TEAE) occurs in a subject dosed with NAL ER during the study that, in the opinion of the Investigator, raises concerns about the safety and tolerability of a higher dose. In addition, the following dose escalation rules will apply.
 
Dose-limiting toxicity (DLT) in the hepatic impaired subject population participating in this study is defined as the dose at which a confirmed Grade 3 adverse event develops in any 2 subjects, even if in two different organ systems, that is IP related and is unlikely to be related to the disease process. Overnight oximetry that drops more than 10% from a subject's baseline lowest value for a consistent period of 5 minutes will be considered a DLT TEAE.
 
Any subject who experiences a DLT TEAE will not receive further doses of study drug, and safety follow-up procedures will be performed.
 
Part 1 (SAD) Dose Escalation Procedures and Stopping Criteria for Subjects with Mild and Moderate Hepatic Impairment (Group 1 and Group 2)
 
Upon completion of the dosing of subjects with mild and moderate hepatic impairment in each of Cohorts 1 to 4 in Part 1 of the study, the safety data and nalbuphine PK parameters will be reviewed by the Safety Committee to determine the continuation of the progression of Part 1 dose escalation and to evaluate the safety for that dose level to be included in Part 2 of the study (MAD).
 
If in the judgement of the Safety Committee the Part 1 PK data demonstrates dose linearity across the dose range in both the mild and moderate hepatic impairment subjects (Group 1 and Group 2 subjects), such that PK modeling can be predictive of steady state dosing levels, a decision may be made to end the study without conducting Part 2 of the study.
 
If 2 subjects develop a DLT at the same dose, then that dose will be confirmed as DLT.
 
If 2 subjects develop a DLT at 2 different doses (eg, 108 mg and 162 mg), then the higher of the 2 doses (162 mg in this example) will not be pursued in remaining Group 1 and Group 2 subjects (if not already dosed).
 
Part 1 (SAD) Dosing Procedures in Cohort 5 (Healthy Volunteers)
 
Cohort 5 will receive the highest dose tested in subjects with mild or moderate hepatic impairment (Cohorts 1 to 4), and if any dose is confirmed to be a DLT during dosing of Cohorts 1 to 4, then that dose will not be studied in Part 1 (SAD) in Cohort 5.
 
Part 1 (SAD) Dose Escalation Procedures and Stopping Criteria for Subjects with Severe Hepatic Impairment (Group 3)
 
Severe Hepatic Impairment (Group 3 Subjects) will receive a single dose of NAL ER 27 mg.

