Across the PN subject population studied in TR03 and TR03EXT, a total of 3 subjects had SAEs while receiving NAL ER, and none were considered related to investigational product (1 motor vehicle accident occurring on icy roads, and 2 cases involving complications or worsening of baseline co-morbidities). As would be expected for an end-stage renal failure population receiving hemodialysis (HD), SAEs were more frequent in the UP studies, and 5 deaths occurred. An immediate cause of death related to the underlying disease or known co-morbidities was clearly identified in each case. The mortality rate across the 2 UP studies (Study TR02 and Study TR02EXT) was consistent with that reported in the literature for HD. One subject had 2 convulsions, 1 during TR02 and a second incidence in TR02EXT; this individual had a history of acquired immune deficiency syndrome (AIDS) with opportunistic infections and a prior stroke, and the seizures were not attributed to the investigational product (see current edition of the IB for a discussion of all the SAEs that occurred in the UP subject population in the NAL ER development program).¹

In the administration of NAL ER to healthy subjects in previous phase 1 studies, the incidence of AEs in the absence of titration was dose dependent. Across the doses of 54 mg, 108 mg, and 162 mg, there is an overall dose-response relationship between dose and specific AE frequencies. Somnolence occurs in > 5% in all 3 higher dose groups (range from 6.2% to 14.8%) and vomiting occurs in > 10% (range from 12.4% to 30.4%). Other events that occur at frequencies > 15% in the 3 higher dose groups are: dizziness (range from 16.9% to 29.10%), headache (15.8% to 21.5%), nausea (17.7% to 36.7%), and somnolence (6.2% to 14.8%).¹

Overall, the Sponsor considers that the risk to subjects in clinical trials of NAL ER is low. This assessment is based on the safety margins established in animals, the known safety profile of the nalbuphine injectable drug product that has been in clinical use for almost 40 years, and the clinical experience to date with the NAL ER and earlier extended-release tablet formulations. The potential benefit that NAL ER may offer by improving severe itch in debilitating conditions is considered to outweigh the potential risks of a clinical trial.

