5.2.1 Rationale for a Single- and Multiple-Escalating Dose Design

This study will include both a single-ascending-dose (SAD) portion and a multiple-ascending dose (MAD) portion. The PK, safety, and tolerability of single ascending doses (SAD) of NAL ER (4 dose levels) will be evaluated in subjects with mild and moderate hepatic impairment. Severe hepatic subjects will be evaluated at a single dose of 27 mg.

The purpose of the SAD will be to assess the safety and PK parameters of the given dose levels in hepatic impaired subjects relative to a selected healthy subject control population as part of the overall NAL ER development program. The SAD will also allow a better understanding of the safety, tolerability and expected steady state PK characteristics in mild and moderate hepatic impairment prior to undertaking safety and itch suppression efficacy studies in this patient population.

In the MAD portion of this study, PK assessment will be carried out at steady state at each respective dose level at steady state during the titration over 13 days up to the highest planned therapeutic dose of 162 mg. It is well documented, in clinical practice and the opiate literature, that gradually increasing the dose of drug with a structured titration can reduce the frequency and severity of the expected AEs associated with initiation of therapy. The NAL ER clinical program utilizes this type of structured titration strategy, starting with once per day dosing at the 27 mg dose of NAL ER, and increasing the dose in a stepwise manner over the next 13 days to the target investigational dose of 162 mg twice daily. Pharmacokinetic steady state is reached after 2 to 3 days of 162 mg twice daily.

Once the Part 1 SAD portion of the study is completed, if in the judgement of the Safety Committee the PK data demonstrates dose linearity across the dose range in both the mild and moderate hepatic impairment subjects (Group 1 and Group 2 subjects), such that PK modeling can be predictive of steady state dosing levels, a decision may be made to end the study without conducting Part 2 of the study.

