8.1 Sample Size

Up to a maximum of 94 adult male or female subjects, ≥ 18 and ≤ 80 years of age are planned to be dosed.

Subjects who withdraw or are withdrawn from the study after dosing, for reasons other than safety and tolerability, may be replaced after consultation between the Investigator and Sponsor. The total number of subjects dosed (including potential replacement subjects) will remain within a maximum of 94 subjects for the whole study (up to 78 subjects in the SAD and up to 16 subjects in the MAD).

The study will enroll up to 8 subjects in Part 2 of the study (MAD) with moderate Child-Pugh categories. An effort will be made to enroll subjects who self-categorize as having some itch (WI-NRS mean score of ≥ 3 at screening). Worst itching intensity scores will be recorded twice daily as specified in the schedule of events. WI-NRS will be used to determine the severity of itch in the hepatic subjects.

8.2 Inclusion Criteria for Subjects with Hepatic Impairment (Cohorts 1 to 4 and 6)

Subjects enrolled in this study will be members of the community at large. Subjects must meet all of the following criteria to be included in the study:

- 1) Male or female with stable hepatic impairment, non-smoker and/or light smoker (up to 5 cigarettes or equivalent/day), ≥ 18 and ≤ 80 years of age, with BMI ≥ 18.0 and ≤ 40 kg/m² and body weight ≥ 50.0 kg for males and ≥ 45.0 kg for females.
- 2) Physical signs consistent with a clinical diagnosis of liver cirrhosis (eg, liver firmness to palpation, splenic enlargement, spider angioma, palmar erythema, parotid hypertrophy, testicular atrophy, or gynecomastia) or prior liver biopsy showing hepatic cirrhosis or prior liver imaging (eg, computed tomography, ultrasound, magnetic resonance imaging) or laboratory tests consistent with hepatic cirrhosis.
- 3) Have mild (Child-Pugh class A, score of 5-6 points), moderate (Child-Pugh class B, score of 7-9 points), or severe (Child-Pugh class C, score of 10-15 points) hepatic impairment at screening.
- 4) The absence of clinically significant unstable cardiovascular, pulmonary, gastrointestinal, hematologic, neurological or psychiatric illness as determined by the Investigator.

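### Protocol 9.13 and SAP 3.5 cap subjects dosed at 112; the synopsis and Protocol 8.1 cap the same quantity at 94, and the synopsis cohort maxima sum to 94

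*Protocol*

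**What the plan says.** Four places in the current protocol and one in the SAP limit the number of subjects dosed.

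- Protocol 9.13 and SAP 3.5, on withdrawal and replacement: the number dosed, counting replacements, "will remain within a maximum of 112 subjects for the whole study".
- Protocol synopsis, Subjects: "The total number of subjects dosed (including potential replacement subjects) will remain within a maximum of 94 subjects for the whole study". The Subject Distribution row of the synopsis repeats 94 and adds the split by part.
- Protocol 8.1: again 94, with "up to 78 subjects in the SAD and up to 16 subjects in the MAD".

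The SAP nowhere states 94.

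On severe subjects, the synopsis stopping rules say "Severe Hepatic Impairment (Group 3 Subjects) will receive a single dose of NAL ER 27 mg", and Protocol 5.2.1 says "Severe hepatic subjects will be evaluated at a single dose of 27 mg". Protocol 9.14.3 agrees. The cohort lists in the synopsis, Protocol 7 and SAP 3.1 place severe subjects only in Cohort 1, the 27 mg cohort.

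Other text does not fit that design:

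- The group lists in the synopsis (Subject Distribution), Protocol 9.3 and SAP 3.2 put Group 3 in each of Cohorts 1 to 4. SAP 3.2 also puts it in Cohort 6, where Protocol 9.3 restricts it to the SAD.
- The synopsis, Protocol 7, Protocol 9.4, SAP 3.1 and SAP 3.4 follow the severe-subject text with a sentence about deciding whether this group moves to a higher dose.
- The synopsis (Drug Administration), Protocol 7 and SAP 3.4 describe severe subjects as starting at 27 mg.

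**The concern.** Both figures are stated for the same quantity in nearly the same sentence, and both stand in operative text rather than in the summary of changes. The higher one sits in the section that staff would consult when deciding whether a replacement may be dosed, and it is the only one the SAP gives. A limit on how many people may be exposed to an investigational drug should have one value.

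The group lists and the remarks about further doses for severe subjects are consistent with the larger number and not with the current design. Correcting the number alone would leave text that describes a different study.

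**Working it through.** **Inputs.** Cohort sizes come from the synopsis, Study Design. They count places, not distinct people, because re-entry is allowed ("Subjects enrolled in Cohort 1 can also be enrolled in Cohorts 2, 3, and 4", and Part 1 subjects may enter Part 2).

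| Cohort | Maximum | Minimum |
|---|---|---|
| 1 (27 mg: mild, moderate, severe) | 8 + 8 + 6 = 22 | 6 + 6 + 4 = 16 |
| 2, 3 and 4 (mild, moderate) | 3 × (8 + 8) = 48 | 3 × (6 + 6) = 36 |
| 5 (healthy) | 8 | 6 |
| SAD subtotal | 78 | 58 |
| 6 (MAD: mild, moderate) | 8 + 8 = 16 | 6 + 6 = 12 |
| Total | **94** | **70** |

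**Step 1: reproduce 94.** The maxima give 78 + 16 = 94, matching the stated cap and its split exactly.

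**Step 2: try to reproduce 112.** The current design does not give it: 112 − 94 = 18, and 18/94 = 19%. Counting 6 severe subjects in all four SAD cohorts does: 4 × (8 + 8 + 6) + 8 + 16 = 112. The excess is 3 further dose levels × 6 severe subjects = 18.

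**Step 3: test other readings of the text.**

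- Protocol 7 and SAP 3.1 give Cohort 6 as 6-8 subjects with mild and moderate impairment, without saying that this is per group. One sentence of Protocol 8.1 mentions up to 8 subjects in the moderate category only, although the same section states 16 for the MAD. Read as 8 in total, the sum is 78 + 8 = 86, or 4 × 22 + 8 + 8 = 104 with severe subjects at all four doses.
- SAP 3.2 taken literally, with severe subjects in Cohorts 1 to 4 and 6, gives 4 × 22 + 8 + 22 = 118.

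Of these readings, only severe subjects in all four SAD cohorts plus 16 in the MAD gives 112.

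**Step 4: side check on room under 94.** The synopsis doses Cohort 5 "to obtain 6-8 subjects who did not vomit within 6 hours of dosing or have any episode of vomiting", so more than 8 healthy subjects may be dosed, while 94 counts 8. Assume that the vomiting rates in Protocol 5.1.1.1 (12.4% to 30.4% across 54, 108 and 162 mg in untitrated healthy subjects) apply.

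- For 8 subjects without vomiting: 8/(1 − 0.124) = 9.1 to 8/(1 − 0.304) = 11.5 dosed on average, which is 1.1 to 3.5 more than counted.
- For 6: 6/(1 − 0.124) = 6.8 to 6/(1 − 0.304) = 8.6.

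**The case against.** The main objection is that little turns on this. No estimate, contrast or power statement uses the cap. The sample size section and the synopsis already carry 94 with a split that adds up, and the SAP repeats 112 only in its description of the study. Nor is either limit likely to bind: with full cells and full re-entry, only 8 + 8 + 6 + 8 = 30 distinct people would be dosed. All of that stands, and it limits the consequence. It does not make two ceilings on one quantity consistent, and re-entry is permitted rather than required.

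A reader might infer that 112, together with the group lists and the remarks about a next dose, exposes severe subjects to doses above 27 mg without adequate stopping rules. The documents do not support that. The synopsis, Protocol 5.2.1 and Protocol 9.14.3 each fix a single 27 mg dose. The synopsis (Drug Administration) and Protocol 9.4 bar the Safety Committee from exceeding the dose outlined for a cohort, and severe subjects are listed by dose only in the 27 mg cohort. Protocol 9.14.3 also ties the Group 3 rules to toxicity already seen in Groups 1 and 2. What remains is inconsistent wording, not authority to escalate.

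A reader might also infer that 94 is too small once vomiting in Cohort 5 is allowed for. That needs every cell full, no re-entry, and a target of 8 rather than the 6 the protocol accepts. The cohort minima sum to 70, leaving 94 − 70 = 24 places, and about 4 places filled by returning subjects would cover the 3.5 on average, before other replacements. This is a question for the sponsor, not a shown defect.

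**Conclusion.** The stated maximum of 112 in Protocol 9.13 and SAP 3.5 is wrong for the current design. The figure that matches the cohort structure is 94, so the stated limit is 18 subjects (19%) too high. It should be corrected because it is an operative limit on exposure and the only one in the SAP, but no planned analysis changes.

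The conclusion rests on the synopsis count for Cohort 6 (up to 8 mild plus up to 8 moderate), which the stated 16 for the MAD supports. The looser Cohort 6 wording in Protocol 7, Protocol 8.1 and SAP 3.1 needs correcting too, or the 94 will itself be open to dispute.

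That 112 survives from a design with severe subjects at all four doses is an inference from the exact match. The documents do not state its origin, and the conflict stands whatever it was.

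**What to change.** 1. Change 112 to 94 in Protocol 9.13 and SAP 3.5.
2. State Cohort 6 as 6-8 mild plus 6-8 moderate, up to 16 in total, in Protocol 7, Protocol 8.1 and SAP 3.1.
3. Limit Group 3 to Cohort 1 in the synopsis (Subject Distribution), Protocol 9.3 and SAP 3.2. This also removes it from Cohort 6 in SAP 3.2.
4. Delete the sentence on moving this group to a further dose level in the synopsis (Study Design), Protocol 7, Protocol 9.4, SAP 3.1 and SAP 3.4.
5. For severe subjects, replace the wording that they start with 27 mg by wording that they are dosed at 27 mg, in the synopsis (Drug Administration), Protocol 7 and SAP 3.4.
6. As a side check only, the sponsor may confirm that 94 leaves room for Cohort 5 subjects who vomit and for replacements. If it does not, one revised cap should appear in every place.

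The cost is wording edits in the two documents and, if wanted, one sponsor confirmation. No new data are needed, and neither the design nor the analysis changes.
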